## 17. ASSESSMENT OF EFFICACY

Efficacy will be assessed in an exploratory fashion. In general, efficacy will be based on changes from baseline to each post-baseline visit (through the end of treatment at Week 26). The following parameters will be measured at all study visits (except the Screening visit):

- Limb water content, by Bioelectrical impedance spectroscopy (BIS): Multiple frequency BIS (L-dex) provides accurate relative measures of protein-rich fluid in the upper limb of patients. BIS is a non-invasive technique that involves passing an extremely small electrical current through the body and measuring the impedance (or resistance) to the flow of this current. The electrical current is primarily conducted by the water containing fluids in the body. BIS quantifies the amount of protein-rich fluid in lymphedema by comparison of the affected to the non-affected limb.
- Limb volume (perometry): Relative limb volume is measured by perometry. Perometry is a non-invasive technique involving a Perometer (Pero-System), which uses infrared light to scan a limb and obtain measurements of the limb's circumference. The truncated cone tape measure method can be used as a backup if the Perometer is unavailable, or not working at time of the patient visit.
- Tissue dielectric constant (MoistureMeterD): The TDC measures the local tissue water content under the skin at various depths ranging from skin to subcutis. The results are converted into a 0% to 100% scale to reflect subcutaneous fluid deposition that can occur in early stage lymphedema.
- Tissue firmness (tonometry/SkinFibroMeter): A tonometer device is pressed into the skin to measure the amount of force required to make an indent in the tissue. The resulting measurement gauges the degree of firmness or fibrosis (tissue scarring) under the skin to assess the severity of lymphedema. (*r*) at dorsal surface of arm 10 cm below the elbow.
- Visual analog scales for pain, swelling, discomfort, and function: This graphic scale has a straight line with endpoints of 0 and 10 that is marked by the patient to calibrate to their extreme limits of pain, swelling, discomfort and function, ranging from “not at all” to “as bad as it could be”. The higher marks on the line indicates the worse condition.

Additionally, health-related QoL assessments will be collected to assess the following:

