- LYMPH-Q ([Appendix 2](#)): This is a patient completed questionnaire that measures the degree of symptoms, function, and psychological impact with patients who have upper extremity lymphedema. Symptoms are rated on a 15-item scale (severe, moderate, mild to none) to measure how the arm feels, the function portion is measured on a 12-item scale (extremely difficult, moderately difficult, a little difficult and not at all difficult) to determine arm function capability, and the psychological portion is measured on a 12-item scale (always, often, sometimes, never) to evaluate how a patient feels having lymphedema.
- LYMQOL ([Appendix 3](#)): This is a patient completed questionnaire that assesses upper limb lymphedema and symptoms, and ability to perform common functional

activities in patients with BCRL. It addresses the following four domains – Symptoms, Body Image/Appearance, Function, and Mood. Each item is scored as 1 = Not at all; 2 = A little; 3 = Quite a bit; and 4 = A lot. Total scores for each domain are summed and divided by the total number of completed question responses. The overall QoL item ranges from 1 to 10. Lower scores indicate a higher QoL.

- Patient Interviews: Patients will be asked to participate in the qualitative interviews. The interviews will occur during screening and/or after completion of blinded treatment. The sample size was elected to be in line with best practice recommendations for cognitive debriefing of existing measures to provide evidence of content validity. Participants recruited for qualitative interviews will match the main inclusion and exclusion criteria found in the trial protocol (BCRL patients that have at least 6 months and no more than 15 years since the most recent type of breast cancer related surgery, have unilateral upper arm lymphedema no greater than 4 years).

The interviews will begin with concept elicitation using a set of open-ended questions that ask the patients to spontaneously identify the BCRL symptoms and daily activity impacts they experience. These data will be compared with the content of the existing instruments to determine whether they are complete and relevant in this target population.

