## **21.7. Efficacy Endpoints**

Analysis of clinical assessments and potential progression or disease will be explored. Comparisons between LYT-100 and placebo will be based on clinical interpretation of effect, magnitudes of effect, and a preponderance of evidence. Estimates of changes over time from these data may be used to power future clinical studies.

Lymphatic obstructions and subsequent edema will be measured using each of the following metrics:

- Limb water content (BIS)
- Limb volume (truncated cone tape measure and/or perometry)
- Tissue dielectric constant (MoistureMeterD)
- Tissue firmness (tonometry/SkinFibroMeter)

For each of these metrics, use of a mixed model for repeated measures (MMRM) will be used to provide model-based estimates of changes over time in each of these outcomes. Descriptive statistics will also be provided at each time point. Details for the model (including covariates to be included) will be provided in the SAP.

The number of occurrences of cellulitis and lymphangitis within the treatment period will be tabulated.

Visual analog scales for pain, swelling, discomfort, and function, and QoL assessments using the LYMPH-Q ([Appendix 2](#)) and LYMQOL ([Appendix 3](#)) questionnaires will be provided at baseline and treatment period timepoints. Both an MMRM and descriptive statistics will be used to describe the outcomes over time, considering each of their respective domains as listed in [Section 17](#).

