## APPENDIX 3: Lymphedema Quality of Life Tool, Arm (Sample)

The score for the individual responses are given below. If the item is not scored and left blank or not applicable this is scored with a 0. Domain totals are calculated by adding the individual scores and dividing the total by the number of questions answered. (If >50% of questions per domain are not answered this cannot be calculated and =0).

The four domains and their corresponding questions are: Function I (a–h), 2, 3;  
Appearance 4, 5, 6, 7, 8; Symptoms 9, 10, 11, 12, 13, 14; and Mood 15, 16, 17, 18, 19, 20.  
Overall quality of life (Q21) is scored as the value marked by the patient, between 0–10.

(1) How much does your swollen arm affect the following daily activities?				
	Not at all	A little	Quite a bit	A lot
a) occupation	1	2	3	4
b) housework	1	2	3	4
c) combing hair	1	2	3	4
d) dressing	1	2	3	4
e) writing	1	2	3	4
f) eating	1	2	3	4
g) washing	1	2	3	4
h) cleaning teeth	1	2	3	4
(2) How much does it affect your leisure activities/social life?				
	1	2	3	4

Please give example(s) of this.

.....

.....

(3) How much do you have to depend on other people?	1	2	3	4
(4) How much do you feel the swelling affects your appearance?	1	2	3	4
(5) How much difficulty do you have finding clothes to fit?	1	2	3	4
(6) How much difficulty do you have finding clothes you would like to wear?	1	2	3	4
(7) Does the swelling affect how you feel about yourself?	1	2	3	4
(8) Does it affect your relationships with other people?	1	2	3	4
(9) Does your lymphoedema cause you pain?	1	2	3	4
(10) Do you have any numbness in your swollen arm?	1	2	3	4
(11) Do you have any feelings of 'pins and needles' or tingling in your swollen arm?	1	2	3	4
(12) Does your swollen arm feel weak?	1	2	3	4
(13) Does your swollen arm feel heavy?	1	2	3	4
(14) Do you feel tired?	1	2	3	4
In the past week	1	2	3	4
(15) Have you had trouble sleeping?	1	2	3	4
(16) Have you had difficulty concentrating on things, e.g. reading?	1	2	3	4
(17) Have you felt tense?	1	2	3	4
(18) Have you felt worried?	1	2	3	4
(19) Have you felt irritable?	1	2	3	4
(20) Have you felt depressed?	1	2	3	4
(21) (24) Overall, how would you rate your quality of life at present? Please mark your score on the following scale:	1	2	3	4

Poor	0	1	2	3	4	5	6	7	8	9	10	Excellent
------	---	---	---	---	---	---	---	---	---	---	----	-----------

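### Section 17's rule that lower LYMQOL scores are better is reversed for the overall quality-of-life item (Q21), which Appendix 3 runs from 0 = Poor to 10 = Excellent

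*Combined protocol and SAP*

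**What the plan says.** Section 17 names four LYMQOL domains (symptoms, body image/appearance, function, mood) and gives the item coding: "Each item is scored as 1 = Not at all; 2 = A little; 3 = Quite a bit; and 4 = A lot". Each domain score is the sum of its items divided by the number of completed responses. The paragraph then closes with two sentences: "The overall QoL item ranges from 1 to 10. Lower scores indicate a higher QoL". The direction rule, "Lower scores indicate a higher QoL", makes no exception for the overall item.

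Appendix 3, which Section 17 cites for this questionnaire, says: "Overall quality of life (Q21) is scored as the value marked by the patient, between 0–10". The line printed on the form reads: "Poor 0 1 2 3 4 5 6 7 8 9 10 Excellent". No reverse scoring is specified.

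For the visual analog scales and both quality-of-life questionnaires, Section 21.7 plans: "Both an MMRM and descriptive statistics will be used to describe the outcomes over time". It refers back to Section 17 for the domains. Section 21 adds that Cohen's D will be calculated for efficacy and other endpoints as the data warrant, and that the values may inform the size or power of later studies. LYMQOL is a secondary endpoint in Section 8.2.

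**The concern.** The only sentence in Section 17 on the direction of LYMQOL stands directly after the description of the overall item, so a reader will naturally apply it to that item. The form says the opposite. The two places also disagree on whether the scale starts at 0 or at 1.

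The trial tests no hypotheses. Section 21 says its conclusions will rest on descriptive results, the magnitude of treatment effects and the overall weight of the evidence on benefit and risk. In that setting the direction of an effect is itself part of the evidence, and no pre-specified test direction would expose a sign read the wrong way. If Section 17 were followed as written, an improvement in patients' own rating of their quality of life would count against the arm in which it occurred. A Cohen's D carried into later planning could be labelled the wrong way as well.

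**Working it through.** The documents give no sample size, power or error rate that bears on this point, so there is no figure to reproduce. The check compares the direction and range given in each place.

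**Domain scores.** Items are coded 1 to 4, with higher meaning more trouble (Section 17). Take a six-question domain; symptoms and mood each have six in Appendix 3.

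- Every answer at the best level: (6 × 1) / 6 = 1.0.
- Every answer at the worst level: (6 × 4) / 6 = 4.0.

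Lower is better, so the rule is correct for the domains.

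**Overall item (Q21).**

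| | Section 17, read literally | Appendix 3 |
|---|---|---|
| Range | 1 to 10 | 0 to 10 |
| Best value | 1 | 10 (Excellent) |
| Worst value | 10 | 0 (Poor) |
| Change from 5 to 8 (8 − 5 = +3) | 3 points worse | 3 points better |

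The directions are opposite. A mark of 0, which the form allows, also lies outside the range in Section 17.

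**Effect size.** Cohen's D = between-arm difference / SD. The documents give neither quantity for Q21, so the following is an illustration on assumed values: one arm gains 1 point more than the other, with an SD between 1.5 and 2.5.

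- SD 1.5: 1 / 1.5 = 0.67
- SD 2.0: 1 / 2.0 = 0.50
- SD 2.5: 1 / 2.5 = 0.40

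Under the Appendix 3 anchors these are benefits of 0.67, 0.50 and 0.40 SD for the arm that gains. Under the Section 17 sentence the same numbers are read as worsening of the same size. The computed value is identical in each case; the conclusion drawn from it is not.

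**Other scales.** For the visual analog scales Section 17 says: "The higher marks on the line indicates the worse condition". This covers all four scales, function included, and the upper anchor is worded as the bad end, so 0 is best and 10 is worst. LYMPH-Q items in Appendix 2 run from 1 at the worst answer to 4 at the best, so higher is better. Section 17 states no direction for LYMPH-Q and therefore misstates none. Neither instrument shows the contradiction found for Q21.

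**The case against.** The strongest defence is that the sentence was meant for the domains, where it is correct, and that the Poor and Excellent anchors on the form settle Q21 for anyone who looks. Nothing is recoded, so the database, the model estimates and the computed Cohen's D are the same either way. An error in the report would need an analyst or reader to follow the sentence and ignore the form. Most of this stands, and it limits the consequence. It does not remove the contradiction: the sentence carries no restriction to the domains and follows immediately on the overall item.

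A second defence is that Section 21.2 lets the SAP override the protocol's statistical methods, and that a SAP is the natural home for scale direction. That is fair, but the protocol describes a SAP still to be written, and the text available contains no direction rule for Q21.

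A third is that Q21 is one item among many exploratory secondary measures, and that Section 21.7 models the questionnaires by domain. Q21 is not one of the four listed domains, so whether it enters the mixed model at all is not established. This also stands. It is a reason to say explicitly how Q21 will be reported.

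A reader might infer more than the documents support:

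- That the direction rule is wrong for LYMQOL as a whole. It is correct for the four domains.
- That the function visual analog scale can be scored either way. Its direction is stated. A patient might find the lower anchor awkward for function, but the patient form is not reproduced, so misreading cannot be shown, and any dilution figure would rest on an invented misreading rate.
- That the opposite coding of LYMPH-Q and the LYMQOL domains is an error. They are separate instruments, each with its coding printed, and the protocol does not pool them.

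**Conclusion.** The point holds for the overall quality-of-life item alone. Section 17 and Appendix 3 contradict each other on its direction (lower better against higher better) and on its range (1 to 10 against 0 to 10). Section 17 is wrong as written, if Appendix 3 shows the form patients complete.

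The size of the problem is a complete reversal of interpretation for Q21, with no change in the data or in the magnitude of any estimate. The 5-to-8 example follows directly from the two scales. The 0.40 to 0.67 SD range rests on the assumed 1-point difference and assumed SDs, and only illustrates that reversal.

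The consequence is modest, because this is one item in an exploratory set with no formal testing. It still deserves correction before analysis: LYMQOL is a listed secondary endpoint, and the trial's conclusions depend on the direction and size of effects.

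**What to change.** In Section 17:

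- Limit the statement that lower scores mean better quality of life to the four LYMQOL domain scores.
- State that the overall item (Q21) runs from 0 (Poor) to 10 (Excellent), with higher better, and correct the range to match Appendix 3.
- State that Q21 is reported separately from the domains.

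As a convenience, the SAP can list the direction of each scale beside its Cohen's D, including that higher is better for LYMPH-Q, so that the sign of every effect is read the same way by everyone.

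The cost is a sentence or two in the protocol and, optionally, a short convention in the SAP. No form, visit, data item or model changes, and no data need to be collected again.

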## **18. STUDY COMPLETION AND DISCONTINUATION**

### **18.1. Patient Withdrawal**

In accordance with applicable regulations, a patient has the right to withdraw from the study, at any time and for any reason, without prejudice to his future medical care.

If a patient is withdrawn because of an AE, the Investigator must arrange for the patient to have appropriate follow-up care until the AE is resolved or has stabilized. Unresolved AEs will be followed until the last scheduled follow-up visit or until the PI and MM determine that further follow-up is no longer indicated. In addition to AEs, other reasons for removal of patients from the study might include, but are not limited to, withdrawal of consent, administrative decision by the Investigator or the Sponsor, protocol deviation, or patient noncompliance.

If a patient asks or decides to withdraw from the study, all efforts will be made to complete and report the observations, especially the listed primary and secondary objectives, as thoroughly as possible up to the date of withdrawal. The primary reason for withdrawal will be identified and recorded on the appropriate eCRF, along with the date of withdrawal.

### **18.2. Patient Replacement**

Patients enrolled who withdraw consent or discontinue for other reasons will not be replaced.

## **19. TERMINATION OR SUSPENSION OF THE STUDY**

The Sponsor, Investigator, and the IRB/IEC reserve the right to terminate or suspend the study at any time; however, this should be discussed between the relevant parties beforehand and the reason for such decision recorded. Should this occur, all data available will also be recorded in the eCRFs. The Investigator should notify the relevant IRC/IEC in writing of the study's completion or early discontinuation.

## **20. DIRECT ACCESS TO SOURCE DATA/DOCUMENTS**

### **20.1. Study Monitoring**

Before an investigational site can enter a patient into the study, a representative of the Sponsor will visit the investigational study site to:

- Determine the adequacy of the facilities.
- Discuss with the Investigator(s) and other personnel their responsibilities with regard to protocol adherence, and the responsibilities of the Sponsor or its representatives. This will be documented in a Clinical Study Agreement between the Sponsor and the Investigator.

The Sponsor has appointed Novotech to manage and monitor the study so as to assure them of the adequate conduct of the study and to act as the contact with the investigational site. A study monitor will be identified and will be responsible for liaison with, and support of, the investigational site.

The study monitors and the regulatory authority inspectors are responsible for contacting and visiting the investigative site for the purpose of inspecting the facilities and, upon request, inspecting the various records of the study (e.g., eCRFs, essential documentation, and other pertinent data) provided that patient confidentiality is respected.

During the study, the monitor will have regular contacts with the investigational site for the following:

- Provide information and support to the Investigator(s).
- Confirm that facilities remain acceptable.
- Confirm that the investigational team is adhering to the protocol, that data are being accurately recorded in the eCRFs, and that study drug accountability checks are being performed.
- Perform source data verification. This includes a comparison of the data in the eCRFs with the patient's medical records at the hospital or practice, and other records relevant to the study. This will require direct access to all original records for each patient (e.g., clinic charts).
- Record and report any protocol deviations not previously sent to the Sponsor.
- Confirm AEs and SAEs have been properly documented on eCRFs and confirm any SAEs have been forwarded to the Sponsor and those SAEs that met criteria for reporting have been forwarded to the IRB/IEC.

The monitor will be available between visits if the Investigator(s) or other staff needs information or advice.

### **20.2. Data Management**

All data will be recorded in individual source documents. An eCRF will be created by the data management group for recording of the required data in the study database. All eCRF

information is to be filled in by site staff as per the eCRF Completion Guidelines. If an item is not available or is not applicable, this fact should be indicated. Blank spaces should not be present unless otherwise directed.

The study monitor will perform source data verification of data entered into the eCRF and raise queries for correction by the site. The data entered into the eCRF will be subject to data validation checks for consistency and completeness by the data management group. Data queries will then be generated and sent to the investigational site for response before the database is locked and released for statistical analysis.

All eCRFs should be maintained on the system with details of any changes logged accordingly.

### **20.3. Audits and Inspections**

Authorized representatives of the Sponsor, a regulatory authority, or an IRB/IEC may visit the site to perform audits or inspections, including source data verification. The purpose of a Sponsor audit or inspection is to systematically and independently examine all study-related activities and documents to determine whether these activities were conducted, and data were recorded, analyzed, and accurately reported according to the protocol, GCP guidelines of the ICH, and any applicable regulatory requirements. The Investigator should contact the Sponsor immediately if contacted by a regulatory agency about an inspection.

## **21. STATISTICS**

A statistical analysis plan (SAP) will be written that will describe, in greater detail, the analyses to be performed. The sections below provide a summary of the general approach to the analysis. The analysis is consistent with the study design and objectives. Note that this study is not hypothesis testing but rather hypothesis-generating, and thus conclusions regarding outcomes will not be based on inferential tests but rather descriptive outcomes, magnitude of treatment effects, and a preponderance of evidence regarding the risk-benefit profile of LYT-100.

As this study is hypothesis-generating, we will calculate effect sizes (Cohen's D, a standardized difference between the treatment arms) for efficacy and other endpoints as the data warrant. These values may be used to estimate sample sizes and/or power estimates for future clinical studies of LYT-100 in this population.

### **21.1. Sample Size**

This study will randomize approximately 50 patients with secondary lymphedema, in a 1:1 ratio to LYT-100 or placebo, as part of this early development and exploratory study of LYT-100. Formal sample size calculations were not performed; rather, the sample size selected should be adequate for preliminary evaluation of safety, tolerability, efficacy signaling, PK, and fibrotic and inflammatory biomarker parameters in the target patient population.

### **21.2. General Statistical Plan**

Statistical methods will be further outlined in an SAP and approved by the Sponsor prior to any analysis. Procedures outlined in the SAP will supersede protocol specified statistical methods in the event of divergence.

The baseline value for all variables will be the last measurement obtained prior to the patient receiving the first dose of study treatment.

Patient disposition (including the number and percent of patients who are enrolled, who receive treatment, who prematurely discontinue and reasons for discontinuation, and who complete the study) will be tabulated by treatment group. Summary statistics for days of exposure and concentration of exposure will be provided by treatment group.

AEs, concomitant medications, clinical laboratory findings, physical examinations, ECGs, and vital signs for each patient will be listed and also summarized in tabular form, as appropriate.

Demographic information will be listed for each patient and summarized. TEAEs and laboratory, vital signs, and ECG parameters will be summarized. In addition, change from baseline will be summarized for laboratory and vital sign parameters. Shift tables will also be provided for clinical laboratory results. ECG results will be classified as normal and abnormal and summarized. ECG results for QTcF will also be classified as < 450 msec, 450 to 500 msec or > 500 msec. Changes in physical exams will be described in the final study report.

In general, descriptive statistics (arithmetic mean, standard deviation [SD], median, minimum, and maximum) will be calculated for continuous valued safety data by specified assessment time point. Frequency summaries (i.e., number and percentage of each observed category) will be provided for categorical and ordinal safety data by treatment and by specified assessment time point.

No formal hypothesis testing will be performed for this study.

